- E:** Vital signs include BP (systolic and diastolic), body temperature, and pulse rate. Blood pressure measurements should be taken in triplicate before all other assessments. Vital signs in general will be collected before any blood samples that are collected at the same time point. At Visit 2 (Day –21), BP will be the only vital sign collected. Instructions for measuring BP will be provided in the Manual of Operations. At Visit 4 (Day 1), vital sign measurements will be taken predose, at 30, 60, and 120 minutes (± 15 minutes) after the first IV dose of IP (before the first SC dose of IP) is administered, then at 30 and 60 minutes (± 15 minutes) after SC dosing.
- F:** Height will be measured at Screening only.

- G:** Electrocardiograms must be performed in triplicate before any blood samples that are collected at the same time point.
- H:** A local assessment of echocardiogram will be performed during Screening unless an echocardiogram was performed for non-study-related reasons within 3 months before Screening.
- I:** At Visit 2 (Day -21), a blood sample will be collected for determination of serum creatinine only.
- J:** A timed 24-hour urine sample will be collected to assess eligibility (ACR) at Screening (Baseline), and to measure CSL346 levels in urine at subsequent indicated visits.
- K:** Subjects will collect urine from their first morning void on 3 consecutive days (2 consecutive days for Visit 9) leading up to and including the morning of each indicated visit.
- L:** Morning midstream urine samples will be collected to evaluate exploratory biomarkers and will also be stored for future research analyses.
- M:** Specific instructions for administration of IP are provided in the IMP Handling Manual. At Visit 4 (Day 1), an initial loading dose of IP will be administered by IV, followed at least 2 hours (but no more than 6 hours) later by the subject's normal prescribed dose by SC infusion. Subsequent doses of IP will be administered by SC infusion.
- N:** Serial blood samples for PK will be collected at Visit 4 (Day 1) predose, at 30 (\pm 5 minutes), 60 (\pm 10 minutes), and 120 (\pm 10 minutes) minutes after the first IV dose of IP (before the first SC dose of IP) is administered, then after the final vital signs measurement. Single PK samples will also be collected at all subsequent visits (before treatment on SC dosing days).

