An overview of identified and potential risks and planned risk mitigation in this phase 2a study is provided in Table 1.

Table 1 Risks and Risk Mitigation

Risk	Potential/ Identified	Source	Risk Mitigation
Injection site reactions	Identified	CSL346_1001 data on file	
 Assessment at study visits Guidance for managing local intolerance
Hypersensitivity / anaphylaxis and infusion reactions; antibody formation	Potential	Class effect of humanized proteins	
 Standard measures Measurement of baseline, mid-, and end of study anti-CSL346 antibody
Weight gain	Potential	Knock-out mouse model [Hagberg et al, 2010]	
 Monitor at study visits
Congenital disorders	Potential	Knock-out mouse model [Bellomo et al, 2000] Preclinical study in quails [Tomanek et al, 2006]	
 Inclusion / exclusion criteria Contraception requirements Pregnancy testing Nonclinical studies in later phases
Renal: acute reversible effect on GFR and / or chronic kidney injury	Potential	Theoretical risk due to VEGF-A modulation [Kamarzarian et al, 2018; Izzedine et al, 2010]	
 Inclusion / exclusion criteria Staged approach for enrollment of subjects with moderate renal impairment Frequent monitoring in first 4 weeks of treatment Measure SCr and evaluate albuminuria at each visit Guidance for managing increases in SCr and albuminuria

Risk	Potential/Identified	Source	Risk Mitigation
Cardiac: myocardial dysfunction with chronic dosing	Potential	Knock-out mouse model [Bellomo et al, 2000] Streptozotocin model [Lal et al, 2017] Theoretical risk due to VEGF-A modulation [Touyz et al, 2018]	
 Exclusion criteria, including baseline assessment of LVEF by ECHO Treatment with SOC Baseline and periodic ECG, BNP, and troponin levels Guidance for managing increases in troponin levels
Increased BP	Potential	Theoretical risk due to VEGF-A modulation [Touyz et al, 2018]	
 Exclusion criteria BP measurement Guidance for managing increases in BP

BP = blood pressure; BNP = b-type natriuretic peptide; ECG = electrocardiogram; ECHO = echocardiogram; GFR = glomerular filtration rate; LVEF = left ventricular ejection fraction; SCr = serum creatinine; SOC = standard of care; VEGF = vascular endothelial growth factor.

2 Study Objectives and Endpoints

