2.3 Exploratory Objectives and Endpoints

2.3.1 Exploratory Objectives

The exploratory objectives of this study are:

1. To explore the effect of CSL346 on the following potential pharmacodynamic (PD) biomarkers:
 - Biomarkers of lipid metabolism
 - Biomarkers of glycemic control
 - Novel plasma, serum, and urinary biomarkers

2. To measure the concentration of CSL346 in the urine and explore its association with albuminuria
3. To explore the relationship between PD biomarkers and CSL346 PK characteristics
4. To evaluate the frequency of subjects with macroalbuminuria (ACR > 300 mg/g [> 33.9 mg/mmol]) at Baseline regressing to microalbuminuria (ACR ≥ 30 and ≤ 300 mg/g [≥ 3.39 and ≤ 33.9 mg/mmol]) or normoalbuminuria (ACR < 30 mg/g [< 3.39 mg/mmol]), or from microalbuminuria to normoalbuminuria
5. To explore possible dose response for the primary and secondary efficacy and safety endpoints

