2.3.2 Exploratory Endpoints

The exploratory endpoints for this study are as follows:

[figure not shown]
1. Changes from Baseline to each assessment in fasting values for the following PD biomarkers:
 - Biomarkers of lipid metabolism including, but not limited to, circulating total cholesterol, triglycerides, high density lipoproteins, low density lipoproteins, glycerol, non-esterified fatty acids, and ketones
 - Biomarkers of glycemic control including, but not limited to, fasting glucose and hemoglobin A1c (HbA1c)
 - Novel biomarkers including, but not limited to, serum-free VEGF-B and soluble tumor necrosis factor receptor 1 (sTNFR1), and urinary VEGF-A, soluble VEGF receptor 1 (VEGF-R1), kidney injury molecule-1, neutrophil gelatinase-associated lipocalin, clusterin, and monocyte chemoattractant protein-1
2. Concentration of CSL346 found in urine at Week 1 (Visit 5) and Week 12 (Visit 9)
3. Number (percentage) of subjects who regress from macroalbuminuria to microalbuminuria or normoalbuminuria, or from microalbuminuria to normoalbuminuria at Week 16 (Visit 10) compared to Baseline

3 Study Design and Oversight

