8.3.2 Urine Samples

Timed 24-hour urine samples are collected for determination of ACR during Screening and for detection of CSL346 in urine at other indicated time points. The subject should collect all urine over a 24-hour period and record start and stop time of the collection period.

FMV urine samples are collected for determination of ACR after Screening. The subject's complete FMV should be collected on 3 consecutive mornings, with the third collection on the morning of the indicated visit. For Week 12, a FMV sample should be collected on 2 consecutive mornings, followed by a 24-hour timed sample, as indicated in Table 9.

Sample collection containers should be kept refrigerated by the subject until brought to the study site.

Midstream urine samples for PD analyses will be collected during regularly scheduled study visits as indicated in the [Schedule of Assessments](#) and in Table 9.

Table 9 Overview of Urine Collections

Visit	Urine Samples Required	Collection Day(s)
Screening (Visit 1)	Timed 24-hour collection	Within 1 week of Visit 1
Screening (Visit 2)	None	--
Week -1 (Day -7 / Visit 3)	FMV x3 Midstream	Day -9, Day -8, Day -7 Day -7 during visit
Day 1 (Visit 4)	FMV x3 Midstream	Day -2, Day -1, Day 1 Day 1 during visit
Day 8 (Visit 5)	Timed 24-hour collection	Morning of Day 7 through morning of Day 8
Week 2 (Day 15 / Visit 6)	FMV x3	Day 13, Day 14, Day 15
Week 4 (Day 29 / Visit 7)	FMV x3 Mid-stream	Day 27, Day 28, Day 29 Day 29 during visit
Week 8 (Day 57 / Visit 8)	FMV x3 Midstream	Day 55, Day 56, Day 57 Day 57 during visit
Week 12 (Day 85 / Visit 9)	FMV x2 Timed 24-hour collection	Day 83, Day 84 Morning of Day 84 through morning of Day 85
Week 16 (Day 113 / Visit 10)	FMV x3 Midstream	Day 111, Day 112, Day 113 Day 113; during visit
Week 24 (Day 169 / EOS)	FMV x3	Day 167, Day 168, Day 169

EOS = End of Study; FMV = first morning void.

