### **10.3 Analysis of Other Secondary Endpoints**

Biomarkers of lipid metabolism, glycemic control and novel biomarkers of kidney function as well as weight will also employ a model similar to the primary endpoint except for the

concentration of CSL346 in urine. The analysis for continuous endpoints is an MMRM analysis of change from baseline to each post-baseline measurement (Weeks 4, 8 and 16). The model will include treatment, stratification related to the concomitant use of SGLT2i, visit (as a categorical factor), and interactions between visit and each of the other model terms, as well as the corresponding baseline measurement as a covariate (refer to [Section 16.1](#) for respective SAS code). Treatment comparisons of interest will be similar to that of the primary endpoint. Lipid parameters will be natural log transformed prior to analysis.

Urinary biomarkers will be normalized for urine creatinine. These urinary biomarkers include urinary VEGF-A, soluble VEGF receptor 1 (VEGF-R1), kidney injury molecule-1 (KIM-1), neutrophil gelatinase-associated lipocalin (NGAL), clusterin, and monocyte chemoattractant protein-1 (MCP-1) and epidermal growth factor (EGF). Normalization is performed by dividing the urinary biomarker by urine creatinine collected at the midstream morning void taken the same day as the urinary biomarker. Normalized urinary biomarkers should be reported in units of pg/ $\mu$ g. To obtain these units, first convert urinary creatinine from units of mg/dL to units of  $\mu$ g/mL by multiplying by 10. Then divide the urinary biomarker (pg/mL) by urinary creatinine ( $\mu$ g/mL) to get normalized results with units of pg/ $\mu$ g.

A repeated measures analysis of covariance model will be employed to analyze the concentration of CSL346 in urine, collected at Day 1, Day 8, and Day 85. The repeated measures analysis of covariance model will include terms for treatment, baseline as a covariate and SGLT2i use.

All analyses for biomarker will be performed on the PD Analysis Set. Analyses for KIM-1, NGAL, EGF and MCP-1 will be performed in addition for the PP Analysis Set. Analyses for urine CSL346 concentration will be performed on the ITT Analysis Set.

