## **14 Pharmacokinetic/Pharmacodynamic Analyses**

A correlation plot  $AUC_{0-28d}$  versus baseline ACR will be provided. The Spearman correlation coefficient, a regression line, and slope and intercept of regression will be added to the plot. The same plot will be provided for CL versus baseline ACR and for  $AUC_{0-28d}$  versus baseline eGFR and for CL versus baseline eGFR.

A correlation plot of  $C_{\text{trough}}$  on Day 29 versus change from baseline in ACR at Day 29 will be provided. The Spearman correlation coefficient, a regression line, and slope and intercept of regression will be added to the plot. The same plot will be provided for the assessment at Days 57, 85, and 113. A similar plot will be provided for CL versus change from baseline in eGFR on Day 29.

A correlation plot of urine CSL346 concentration on Day 8 versus baseline ACR on Day 8 will be provided. The Spearman correlation coefficient, a regression line, and slope and intercept of regression will be added to the plot. The same plot will be provided for urine CSL346

concentration at Day 85 versus ACR at Day 85. A correlation plot of urine CSL346 concentration at Day 85 versus change from baseline in ACR at Day 85 will also be provided. The same series of plots will be provided for urine CSL346 concentration versus baseline eGFR and urine CSL346 concentration versus the change in eGFR.

The correlation of systolic blood pressure, measured at 60min after SC dosing at Visit 4, versus  $AUC_{day1}$ , starting after IV administration, will be presented. The Spearman correlation coefficient, a regression line, and slope and intercept of regression will be added to the plot. The same plot will be provided for diastolic blood pressure.

A correlation plot of systolic blood pressure versus  $C_{trough}$  at Day 29 will be provided. The Spearman correlation coefficient, a regression line, and slope and intercept of regression will be added to the plot. The same plot will be provided for the assessments at Days 57, 85, and 113. A similar series of plots will be provided for diastolic blood pressure versus  $C_{trough}$  at Days 29, 57, 85, and 113.

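### SAP 14 ties the Day 8 urine CSL346 plot to an ACR that is not collected on Day 8, and urine CSL346 is analysed only as raw concentration, so urine volume adds avoidable noise to an exploratory question

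*SAP*

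**What the plan says.** Protocol 2.3.1 gives the objective: "To measure the concentration of CSL346 in the urine and explore its association with albuminuria". The matching endpoint in 2.3.2 is the urine concentration at Week 1 (Visit 5) and Week 12 (Visit 9).

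The two quantities come from different urine samples. Protocol 8.3.2 says: "Timed 24-hour urine samples are collected for determination of ACR during Screening and for detection of CSL346 in urine at other indicated time points". It then says: "FMV urine samples are collected for determination of ACR after Screening". Note J to the Schedule of Assessments agrees, giving the purpose of the 24-hour sample as "to assess eligibility (ACR) at Screening (Baseline), and to measure CSL346 levels in urine at subsequent indicated visits".

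SAP 14 plans three plots of urine CSL346 against ACR. The first is "A correlation plot of urine CSL346 concentration on Day 8 versus baseline ACR on Day 8 will be provided". The other two set Day 85 concentration against Day 85 ACR and against the change in ACR at Day 85. Similar plots against baseline eGFR and change in eGFR follow. Each carries a Spearman coefficient and a fitted line.

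On scale, SAP 10.3 states: "Urinary biomarkers will be normalized for urine creatinine". It lists seven analytes, and CSL346 is not among them. SAP 10.3 models urine CSL346 as a concentration, and SAP 12.1 summarises it as one.

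**The concern.** There are two separate weaknesses.

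First, the ACR axis of the Day 8 plot is called both baseline and Day 8. A programmer cannot tell which is meant, and one of the two readings has no data behind it.

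Second, a concentration from a 24-hour collection depends on how much urine the subject passed. Two subjects who excrete the same amount of antibody will have different concentrations if their volumes differ. ACR does not have this problem, because dilution cancels in the ratio. Correlating a volume-dependent measure with a volume-free one weakens the association. If volume is itself related to ACR or eGFR, it can also shift the correlation in either direction. At stake is the clarity of an exploratory PK/PD answer drawn from about 50 subjects given CSL346 (25 + 25).

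**Working it through.** The plan gives no figure of its own on this point, so the check sets the schedule against the SAP and then sizes the volume effect under stated assumptions.

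**1. Which urine exists when** (Schedule of Assessments; Protocol Table 9)

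| Visit | Timed 24-hour | FMV samples | Midstream |
|---|---|---|---|
| Screening Visit 1 | yes | 0 | no |
| Visit 3, Day -7 | no | 3 | yes |
| Visit 4, Day 1 | no | 3 | yes |
| Visit 5, Day 8 | yes | 0 | no |
| Visit 9, Day 85 | yes | 2 | no |

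SAP 8.2.7 derives ACR from FMV samples, and the post-baseline visits in SAP 10 are Weeks 2, 4, 8, 12, 16 and 24, without Week 1. So no Day 8 ACR is planned. Baseline ACR does exist (3 + 3 = 6 FMV samples before treatment), and so does Day 85 ACR (2 FMV samples). Of the three plots against ACR, the two at Day 85 can be made. The Day 8 plot can be made only if baseline ACR is meant.

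**2. Whether the SAP's creatinine rule could be extended.** SAP 10.3 uses creatinine from the midstream void taken on the same day. Visits 5 and 9 have no midstream sample, so the rule cannot be applied to CSL346 as it stands.

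**3. Effect of volume at fixed excretion.** Concentration = amount / volume. For 1 mg excreted: 1000 ng/mL in 1 L, 500 ng/mL in 2 L, 333 ng/mL in 3 L.

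**4. Effect on the correlation.** On the log scale, log concentration = log amount - log volume. If volume is independent of amount and of ACR, the correlation with log ACR is multiplied by

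f = s_A / sqrt(s_A² + s_V²),

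where s_A and s_V are the between-subject log SDs of amount and volume. A CV converts by s = sqrt(ln(1 + CV²)). None of these spreads is in the documents, so all are assumptions:

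- amount CV 50%, volume CV 50%: s_A = s_V = 0.472, f = 0.71
- amount CV 150%, volume CV 20%: s_A = 1.086, s_V = 0.198, f = 0.98
- log SDs 0.7 and 0.5: 0.7 / sqrt(0.49 + 0.25) = 0.81
- log SDs 0.7 and 0.4: 0.7 / sqrt(0.49 + 0.16) = 0.87

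The formula is for a linear correlation on the log scale, whereas the SAP reports Spearman. A simulation with log-normal amount and volume and a true log-scale correlation of 0.5 gave Spearman 0.485 falling to 0.342 in the first case (ratio 0.71) and 0.483 falling to 0.475 in the second (ratio 0.98), so the formula carries over.

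**5. A trap in one possible remedy.** If CSL346/creatinine were plotted against albumin/creatinine from the same 24-hour sample, one creatinine value would sit in both denominators. With assumed independent log SDs of 0.7 (CSL346), 1.0 (albumin) and 0.3 (creatinine), the correlation arising with no true association is

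0.3² / sqrt((0.7² + 0.3²)(1.0² + 0.3²)) = 0.09 / sqrt(0.58 × 1.09) = 0.11.

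**The case against.** A reader might infer that objective 2 cannot be answered as planned. The documents do not support that. The objective and endpoint are worded as concentration, both Day 85 plots are feasible, and Day 8 concentration can be plotted against baseline ACR.

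The Day 8 sentence can fairly be called a slip: it does say baseline, and the same paragraph uses baseline eGFR. That is probably right. But the parallel Day 85 plot uses same-day ACR, so the intended axis is not certain and the text needs correcting.

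A reader might also see the absence of CSL346 from the normalisation list as an internal contradiction. It is not: that rule is for spot midstream samples, and CSL346 comes from timed collections. What stands is that a timed collection offers its own correction, the amount excreted, and the SAP does not ask for it.

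Protocol Table 1 lists as risk mitigation: "Measure SCr and evaluate albuminuria at each visit". This is a safety summary and creates no ACR at Visit 5. It does not match the schedule there and should be reconciled, but it does not bear on the plots.

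Finally, the size of the attenuation is wholly assumed, and the plots are descriptive and feed no test. Both points stand, and they keep this a small matter. Protocol 8.3.2 mentions recording start and stop times but not volume. The laboratory manual may cover volume and was not available, so it cannot be said that volume goes unrecorded.

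**Conclusion.** The point holds in a limited form. That the Day 8 plot is mis-specified follows from the documents alone. The use of raw concentration, with no volume or creatinine term, is also plain from the text. Its consequence is lost precision: a multiplier on the true correlation of 0.71 to 0.98 over the assumed range, which weakens an association without removing it. Bias is possible only if volume is related to ACR or eGFR, on which the documents are silent. Nothing here touches the primary endpoint, its model or the sample size. It is a minor improvement, worth making because it costs little.

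**What to change.** - **SAP 14:** define the first plot as urine CSL346 on Day 8 versus baseline ACR (geometric mean of the pre-dose FMV samples).
- **SAP 10.3, 12.1 and 14:** keep raw concentration and add a dilution-corrected measure beside it. Prefer the amount excreted over the timed collection (concentration × volume) if volume is recorded. This relies on complete collections. Otherwise use CSL346/creatinine, with creatinine assayed in the same 24-hour sample where sample remains; the documents do not say that residual 24-hour urine is kept. State how results below the 80 ng/mL urine quantification limit carry into the new measure.
- **Limits:** do not plot CSL346/creatinine against ACR from the same 24-hour sample without noting the shared denominator. Keep any 24-hour ACR out of the primary model, which uses FMV ACR.
- **While SAP 10.3 is open:** it names Day 1 as a urine CSL346 collection day, but the schedule has no 24-hour urine then and Protocol Table 7 places the baseline sample at Screening. Reconcile the two.

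Cost: text changes, a small amount of extra analysis and, only if volume is not recorded, one routine creatinine assay on at most 2 visits × 100 subjects = 200 post-baseline samples (about 100 if limited to CSL346 subjects). No new collection from subjects is needed.

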## 16 Appendices

### 16.1 SAS Code

SAS code for MMRM analysis

```
Ods graphics on;
Proc mixed data=data_set method=reml plots=residualpanel;
  Class treatment visit patient sglti_yn;
  Model chglnacr =treatment visit baseline sglti_yn
  treatment*visit sglti_yn*visit baseline*visit / alpha=0.20 cl
  ddfm=kr covb solution;
  Repeated visit / type=un subject=patient r rcorr;

* *** Estimate for treatment difference at 2 weeks *** *;
  Estimate "CSL08 vs. PBO at 2 weeks" treatment 1 0 -1
  treatment*visit 1 0 0 0 0 0      0 0 0 0 0 0      -1 0 0 0 0 0 / CL
  alpha=0.2;
  ESTIMATE "CSL16 vs. PBO at 2 weeks" treatment 0 1 -1
  treatment*visit 0 0 0 0 0 0      1 0 0 0 0 0      -1 0 0 0 0 0 / CL
  alpha=0.2;
  ESTIMATE "CSL vs. PBO at 2 weeks" treatment 0.5 0.5 -1
  treatment*visit 0.5 0 0 0 0 0      0.5 0 0 0 0 0      -1 0 0 0 0 0 / CL
  alpha=0.2;

* *** Estimate for treatment difference at 16 weeks *** *;
  Estimate "CSL08 vs. PBO at 16 weeks" treatment 1 0 -1
  treatment*visit 0 0 0 0 1 0      0 0 0 0 0 0      0 0 0 0 -1 0 / CL
  alpha=0.2;
  ESTIMATE "CSL16 vs. PBO at 16 weeks" treatment 0 1 -1
  treatment*visit 0 0 0 0 0 0      0 0 0 0 1 0      0 0 0 0 -1 0 / CL
  alpha=0.2;
  ESTIMATE "CSL vs. PBO at 16 weeks" treatment 0.5 0.5 -1
  treatment*visit 0 0 0 0 0.5 0      0 0 0 0 0.5 0      0 0 0 0 -1 0 / CL
  alpha=0.2;

  Lsmmeans treatment treatment*visit / diff cl;
run;
Ods graphics off;
```

Where:

- chglnacr is the repeated measure of change in log ACR collected at Weeks 2, 4, 8, 12, 16 and 24;
- treatment takes on three levels (CSL346 8 mg/kg, CSL346 16 mg/kg and placebo)

- sglt2i\_yn is the stratification variable associated with the presence or absence of a concomitant SGLT2i at entry into the trial;
- baseline is the baseline log ACR used as a covariate in the model;
- visit is the time variable;

#### SAS code for multiple imputation

```
Proc mi data=data_set out=data_set_imputed nimpute=10
seed=xxxx round=0.01;
  Var treatment visit sglti_yn patient chglnacr;
  Monotone reg(chglnacr = treatment visit sglti_yn patient);
run;
```

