If, after Step 2, the subject continues to have mild injection site reactions that are deemed unacceptable by the subject or Investigator, and would otherwise lead to discontinuation of the IP, contact the Study Medical Monitor to discuss and document the appropriate action to be taken for that subject. If the Medical Monitor approves, then move to Step 3 and discontinue further dosing with IP. Every effort should be made to continue the subject's participation in Follow-up Visits even if the IP is discontinued.

For any injection site reaction that exceeds the definition of mild, either in duration or severity of symptoms, the Study Medical Monitor must be contacted to discuss and document the rationale for continuing administration of the IP at a decreased total SC infusion volume and / or dose, or discontinuing further dosing.

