### 10.1.3 Sensitivity Analyses of Primary Endpoint(s)

A sensitivity analysis will be conducted with regard to the primary endpoint. The analysis will be identical to the one identified above, except that the Per Protocol Analysis Set is used. In this analysis, subjects will be assigned to the treatment actually received. In the event of a decrease in dose (from 16 mg/kg to 8 mg/kg) the subject will be assigned to the highest dose treatment received. This analysis will exclude data following major protocol deviations and other factors which may influence the primary outcome. Major protocol deviations will be determined without knowledge of treatment assignment (i.e., prior to unblinding). [Appendix 16.7](#) provides a list of major protocol deviations and other reasons for exclusion from the Per Protocol Analysis Set.

The second (to be conducted for Per Protocol Analysis Set) sensitivity analysis is a tipping point analysis that will employ multiple imputation for missing data (missing change from baseline in ACR) using multiple regression to provide multiple complete data sets [[Buuren 2018](#)]. The same MMRM model will be used to analyze the imputed complete data sets (missing ACR values will be imputed for planned ACR assessments up to the individual subjects last performed visit before EOS and EOS visit). If the original analysis indicates a significant effect, the tipping point analysis adds a value, delta, to the imputation model to assess the sensitivity of the “missing at random” assumption. In this case, the delta is

increased (decreased) until statistical significance is lost. A conclusion of the sensitivity analysis is based on whether the value of delta at the time significance is lost is interpreted as likely given the data observed.

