## 16.7 Factors to be Addressed in Per Protocol Analysis Set

The following define major events which could result in subjects' data being removed from the per protocol analysis set. Subjects' data may be removed completely or from the time of the major event up to the end of subject's study participation.

At a specific time point, ACR measurements are to be used in summaries and analysis as long as there are at least 2 FMVs for that time point (4 FMVs for baseline) available.

- Extrinsic factors with the potential to impact ACR during treatment period. For any such occurrences, data points at or beyond the date of the occurrence will be excluded from analysis. [These data will be provided by CSL.]
  - Protocol deviations:
    - Subjects with substantial change in blood pressure medications or DKD medications;
    - Prohibited concomitant medications;
    - Initiation of lipid lowering agent;
    - Change in SGLT2i doses;
    - Change in dose in agents that impact tubular secretion of serum creatinine (fibrates).
    - Missed intermittent dose
  - Cardiac AESI with heart failure.
- Study drug [to be derived by Parexel]:
  - For subjects receiving fewer than 4 doses of the investigational product, all data on or after the date of the last dose + 4 weeks + 1 day will be excluded. If no dose is administered then all data for that subject will be excluded.
- Violation of study entry criteria. In these cases, all data from these subjects will be excluded from analysis. [These data will be provided by CSL.]
  - Baseline Glycosylated HbA1c  $\geq 12\%$ ;
  - Change in SCr from Visit 1 (<63 Days before Day 1) to Visit 2 (Day -21)  $> 0.3$  mg/dL (26.5  $\mu\text{mol/L}$ );
  - Uncontrolled hypertension: SBP  $> 160$  mmHg or DBP  $> 100$  mmHg prestudy (SBP $>150$  mmHg at randomization).

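### The imputation model printed for the per-protocol tipping-point analysis does not match the MMRM, so delta = 0 need not reproduce the PP-set result, and the handling of Week 16 and the reach of delta are not defined

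*SAP*

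**What the plan says.** SAP 10.1.3 describes two sensitivity analyses of the primary endpoint. The first repeats the MMRM in the Per-Protocol set: "In this analysis, subjects will be assigned to the treatment actually received". The second is a tipping-point analysis in the same set. Missing change in ACR is imputed by multiple regression, the resulting data sets are described as complete, and each is analysed with the same MMRM. The scope of imputation is given as "missing ACR values will be imputed for planned ACR assessments up to the individual subjects last performed visit before EOS and EOS visit". After a significant original analysis, "the tipping point analysis adds a value, delta, to the imputation model", and delta is moved until significance is lost.

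The MMRM code in SAP 16.1 has "Class treatment visit patient sglti_yn", baseline log ACR, the interactions "treatment*visit sglti_yn*visit baseline*visit" and an unstructured within-patient covariance. The multiple-imputation code in the same appendix has the model "Monotone reg(chglnacr = treatment visit sglti_yn patient" and no CLASS statement. SAP 10.4 limits imputation to the sensitivity analysis of the primary endpoint, so this code serves no other purpose.

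Two other rules bear on what is missing. For subjects with fewer than four doses, SAP 16.7 says "all data on or after the date of the last dose + 4 weeks + 1 day will be excluded". Protocol 9.1.3.1 asks for every effort to continue "participation in Follow-up Visits even if the IP is discontinued", and 9.1.3.2 and 9.1.3.3 say the same in substance.

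**The concern.** The tipping delta measures how far the missing values must depart from MAR before the conclusion changes. That reading needs delta = 0 to be the MAR analysis, here the PP-set MMRM. If the imputation model is a different and simpler one, the contrast has already moved before any delta is added.

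The printed code could cause this in two ways. Without CLASS, numeric codes for three-level treatment, visit and patient number enter as straight-line slopes, and character codes make the step fail. Without treatment-by-visit, imputed Week 16 values carry an effect averaged over visits, although the estimand is the Week 16 contrast.

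The text has separate gaps. Read literally, a subject who left the study after Week 8 gets a Week 24 value but no Week 16 value. A subject who stopped dosing but attended Week 16 has that value removed by SAP 16.7, and 10.1.3 does not say whether a removed value is then imputed. No arm or visit is named for delta.

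**Working it through.** **Plan's own figures (SAP 4.4).** SD 0.65 with 47 per pooled arm gives SE = 0.65 × √(4/94) = 0.134. The critical effect is 1.291 × 0.134 = 0.173 (t quantile, 92 df), as stated. Planned drop-out is 6%. The ceiling of 124 randomized for 94 completers allows 1 − 94/124 = 24%. The documents give no PP loss rate, so 6%, 15% and 24% are used as a range.

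**The two models side by side (SAP 16.1).**

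| Feature | MMRM | Imputation code |
|---|---|---|
| Treatment, visit, patient, SGLT2i | categorical | no CLASS statement |
| Baseline log ACR, and by visit | yes | no |
| Treatment by visit | yes | no |
| SGLT2i by visit | yes | no |
| Subject's other-visit ACR | through unstructured covariance | no |

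**Hand calculation.** Assume codes 1/2/3 for 8 mg/kg, 16 mg/kg and placebo (the order in the ESTIMATE statements), 25/25/50 subjects, equal loss in each arm, and Week 16 imputed.

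- Mean code = (25 + 50 + 150)/100 = 2.25. Sum of squares = 25(1.25²) + 25(0.25²) + 50(0.75²) = 68.75.
- For a constant effect of −0.315 in both doses, the cross-product is 25(1.25)(0.315) + 25(0.25)(0.315) = 11.81, so slope = 11.81/68.75 = 0.172.
- The fitted line implies a pooled contrast of 0.172 × (1.5 − 3) = −0.258, which is 0.818 of −0.315.
- Without treatment-by-visit, the effect carried is the average over the six visits. So shift ≈ loss × (0.315 − 0.818 × average effect size).

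Average effect sizes:
- constant: 0.315
- growing (−0.315 × week/16, flat after Week 16): 0.315 × 3.625/6 = 0.190
- waning (multiples 2, 1.8, 1.6, 1.3, 1, 1): 0.315 × 8.7/6 = 0.457

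| Effect pattern | Formula, 6/15/24% loss | Simulated, 6/15/24% loss |
|---|---|---|
| Constant | +0.003/+0.009/+0.014 | +0.004/+0.010/+0.016 |
| Growing | +0.010/+0.024/+0.038 | +0.012/+0.027/+0.039 |
| Waning | −0.004/−0.009/−0.014 | −0.003/−0.013/−0.016 |

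**Simulation behind the last column.** 600 trials per scenario (500 for waning), 100 subjects, exchangeable correlation 0.7, baseline log ACR SD 1 with slope −0.15, monotone completely random loss and 10 imputations. The comparison is with the unstructured-covariance estimate on the same data. The Monte Carlo SE is at most 0.003. Further results at 6/15/24% loss:

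- Unequal doses (−0.21/−0.42), placebo coded last: +0.007/+0.020/+0.026. Placebo coded 0: +0.002/−0.001/0.000.
- Constant effect with dropout depending on the last observed change, odds ratio per 0.65 log units: OR 1.5, +0.005/+0.012/+0.021; OR 2, +0.010/+0.022/+0.034; OR 4, +0.020/+0.053/+0.062.
- Mean absolute shift in a single trial under random loss: 0.022–0.025/0.034–0.044/0.047–0.059. With a matched imputation model it is at most 0.006/0.010/0.014, and mean shifts are within 0.002.
- CLASS added and nothing else: within 0.001 for a constant effect, but +0.016/+0.036/+0.056 for a growing one.

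A second simulation (400 trials per scenario) used correlation falling from 0.84 to 0.41 between visits, an effect building to −0.315 at Week 16, and 124 subjects at 24% loss. Its shifts were +0.008/+0.024/+0.046 under random loss and +0.023/+0.042/+0.058 under outcome-dependent loss. The last is −0.317 against −0.259, or −27% against −23%.

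**Reach of delta.** A subject last dosed on Day 57 loses data from Day 57 + 28 + 1 = Day 86, which includes Week 16 (Day 113). Take the literal reading of 10.1.3, 15% loss, and 1 log unit added to imputed CSL346 values. The Week 16 contrast then moves 0.03 if all loss is study dropout (only Week 24 imputed), 0.10 if half is PP exclusion of attended visits, and 0.15 if all is PP exclusion. The same delta therefore differs about five-fold in effect according to the type of loss and the reading of the text.

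**The case against.** The strongest reply is that this is outline code for a secondary check. The seed is a placeholder, no delta or pooling step is shown, and SAP 3 says practical implementation details will accompany the table shells in a separate document. Character coding would stop the step and be corrected. If patient is treated as a factor, as in the MMRM, it carries each subject's own mean and so most of the baseline and other-visit information; the constant-effect shift is then at most 0.004. At the planned 6% loss, mean shifts are 0.002 to 0.020 in absolute value, and in a 400-trial run significance at delta = 0 changed in about 3–6% of trials. Most shifts go against CSL346. The analysis runs delta only after a significant result, and the primary ITT MMRM uses no imputation. The shifts also presuppose that Week 16 is imputed, which the literal text denies for study dropouts. Protocol 4.3.2 still seeks Visit 10 and EOS data from withdrawn subjects.

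The limits on scope and size stand. The rest does not remove the problem. A separate document cannot quietly override code printed in the SAP. Adding CLASS does not cure a growing effect, because treatment-by-visit is still absent. The two halves are not in conflict: if Week 16 is imputed, the model is wrong for it; if it is not, delta barely reaches the primary contrast for study dropouts. SAP 10.1.3 refers to complete data sets, which favours the first reading. Whether PP-excluded values should be imputed is a choice, but the SAP must state it.

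**Conclusion.** The concern holds and should be fixed. Following the printed code gives a starting point that need not equal the PP-set MMRM, and the text leaves Week 16 and the reach of delta undefined. The size rests on assumptions about loss, effect pattern, correlation and coding that the documents do not supply. At 6% loss it is small, at most 0.023 log units in the scenarios run. At 24%, the most the sample-size plan allows for, it reaches about 0.06, or 0.06/0.134 ≈ 0.4 to 0.5 SE, under strongly outcome-dependent dropout. Direction is usually toward no effect but reverses for a waning effect. The primary analysis and sample size are untouched. The weight comes from this being the only planned test of the MAR assumption.

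**What to change.** In SAP 16.1, replace the imputation code:

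- Use one row per subject.
- Declare treatment (three levels, as assigned in the PP analysis) and SGLT2i stratum as CLASS variables.
- Fill intermittent gaps first, then impute each visit in order from treatment, stratum, baseline log ACR and the subject's earlier visits.
- Drop patient as a predictor. An equivalent model with these terms is acceptable.

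In SAP 10.1.3:

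- State that Week 16 is imputed for study dropouts and for values removed by the PP rules. If the sponsor prefers to leave PP-removed values out, say so explicitly.
- State the arm and visits to which delta applies, and its direction.
- Require a check that delta = 0 agrees closely with the PP-set MMRM before any delta is applied.

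The cost is a few lines of SAP text and appendix code. No new data are needed.
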